#### 13.5 Secondary Objectives, Endpoints, Analysis Plans

The secondary objectives as prioritized in Section 1.2 Secondary Objectives are:

13.5.1 Compare differences in proliferation index (Ki-67) expression from baseline to post-exposure in visually normal appearing oral cavity/oropharyngeal tissue. Absolute change in Ki-67 pre- to post-study treatment and difference in absolute change between the ACTOplus met® XR and placebo subjects will be summarized with descriptive statistics as for the primary endpoint.

13.5.2 Compare immunohistochemical differences from baseline to post-exposure of oral cavity/oropharyngeal adjacent visually normal appearing tissue and tumor tissue samples with regard to the apoptosis biomarker, Cleaved Caspase 3.

13.5.3 Compare immunohistochemical differences from baseline to post-exposure of oral cavity/oropharyngeal tumor tissue samples with regard to Cyclin D1, p21 and biguanide or PPARγ associated pathway biomarkers. Prospective biomarkers on the panel will include but are not limited to pAKT, pAMPK, pS6 (Metformin), and PPARγ.

13.5.4 Compare immunohistochemical differences from baseline to post-exposure of oral cavity/ tumor tissue samples with regard to immune microenvironment (TREG, T4, T8, TAM-CD68+, PD1, PD-L1).

13.5.5 Compare and correlate pre- and post-ACTOplus met® XR treatment Human HT-12 v 4 BeadChip (Illumina) whole transcriptome gene analysis on total RNA samples from oral cavity/oropharyngeal adjacent visually normal appearing tissue and tumor tissue.

13.5.6 Determine HPV status in pre-treatment tumor tissue using p16 immunohistochemistry.

Secondary endpoints will consist of changes from baseline to post-exposure in immunohistochemical markers and gene analysis. Each of these will be summarized for baseline, post-exposure, and absolute change by treatment arm using the appropriate descriptive statistics, and will be evaluated with Student's t-test or Wilcoxon rank-sum test, as with the primary endpoint. As this is an exploratory study, in general, adjustments will not be made for the endpoints tested. The exception is the whole transcriptome gene analysis. Because of the amount of data that will be generated for this, adjustments for multiplicity of comparisons will be made to control the false discovery rate using the methods of Benjamini and Hochberg when testing treatment group differences[62].

13.5.7 In those participants who have had a standard of care staging PET/CT prior to randomization, we will compare the pre- and post-study intervention: SUV (Standardized Uptake Value) of FDG and tumor burden using RECIST v 1.1 between the two treatment arms. Because only a subset of participants will have PET/CT scans performed, this will be an exploratory analysis.

## **13.6 Reporting and Exclusions**

All participants who take any study agent, ACTOplus met® XR or placebo, will be analyzed for adverse events. Subjects that maintain 80% compliance for the time period beginning day 1 and ending on the day before surgical intervention will be considered compliant. Compliance will be measured through pill counts conducted by the pharmacy or an independent 3rd party (not a member of the study team) and reported to the study coordinator for documentation in the Visit Guide. For biomarker modulation, all participants that have evaluable pre- and post-study treatment samples will be included in the analysis. Compliance and availability of evaluable samples for biomarker studies will be included in descriptive statistics.

## **13.7 Evaluation of Toxicity**

All participants will be evaluable for toxicity from the time of their first dose of ACTOplus met® XR or placebo.

## **13.8 Evaluation of Response**

For the primary analysis comparing the absolute change in proliferation index (Ki-67) expression from baseline to post-exposure between treatment arms, an intent to treat analysis will be used. All of the participants who met the eligibility criteria, with the exception of those who did not receive study agent, will be included in the main analysis. Random dropouts will be excluded. Data will be examined for non-random dropouts. An appropriate sensitivity analysis will be conducted in the case of missing data.

## **13.9 Interim Analysis**

There is no planned interim analysis of the primary endpoint of the study. Safety data will be monitored periodically by the Consortium's data monitoring committee.

## **13.10 Ancillary Studies**

Not Applicable

## **14. ETHICAL AND REGULATORY CONSIDERATIONS**

### **14.1 Form FDA 1572**

Prior to initiating this study, the Protocol Lead Investigator at the Lead or Participating Organization(s) will provide a signed Form FDA 1572 stating that the study will be conducted in compliance with regulations for clinical investigations and listing the investigators, at each site that will participate in the protocol. All personnel directly involved in the performance of procedures required by the protocol and the collection of data should be listed on Form FDA 1572.

### **14.2 Other Required Documents**

14.2.1 Current (within two years) CV or biosketch for all study personnel listed on the Form FDA 1572 and Delegation of Tasks form for the Lead Organization and all Participating Organizations.

14.2.2 Current medical licenses (where applicable) for all study personnel listed on Form FDA 1572 and Delegation of Tasks form for the Lead Organization and all Participating Organizations.

14.2.3 Lab certification (*e.g.*, CLIA, CAP) and lab normal ranges for all labs listed on Form FDA 1572 for the Lead Organization and all Participating Organizations.

14.2.4 Documentation of training in “Good Clinical Practice” for all study personnel listed on the FDA Form 1572 for the Lead Organization and all Participating Organizations.

14.2.5 Documentation of training in “Protection of Human Research Subjects” for all study personnel listed on the FDA Form 1572 and Delegation of Tasks form for the Lead Organization and all Participating Organizations.

14.2.6 Documentation of Federalwide Assurance (FWA) number for the Lead Organization and all Participating Organizations.

14.2.7 Signed Investigator’s Brochure/Package Insert acknowledgement form

14.2.8 Delegation of Tasks form for the Lead Organization and all Participating Organizations signed by the Principal Investigator for each site and initialed by all study personnel listed on the form

14.2.9 Signed and dated NCI, DCP Financial Disclosure Form for all study personnel listed on Form FDA 1572 for the Lead Organization and all Participating Organizations

### **14.3 Institutional Review Board Approval**

Prior to initiating the study and receiving agent, the Investigators at the Lead Organization and the Participating Organization(s) must obtain written approval to conduct the study from the NCI Cancer Prevention and Control CIRB, including Study-specific Worksheet (SSW) approval for the participating organizations. Should changes to the study become necessary, protocol amendments will be submitted to the DCP PIO according to DCP Amendment Guidelines. The DCP-approved amended protocol must be approved by the NCI Cancer Prevention and Control CIRB prior to implementation.

#### **14.4 Informed Consent**

All potential study participants will be given a copy of the IRB-approved Informed Consent to review. The investigator will explain all aspects of the study in lay language and answer all questions regarding the study. If the participant decides to participate in the study, he/she will be asked to sign and date the Informed Consent document. The study agent(s) will not be released to a participant who has not signed the Informed Consent document. Subjects who refuse to participate or who withdraw from the study will be treated without prejudice.

Participants must be provided the option to allow the use of blood samples, other body fluids, and tissues obtained during testing, operative procedures, or other standard medical practices for further research purposes. If applicable, statement of this option may be included within the informed consent document or may be provided as an addendum to the consent. A Model Consent Form for Use of Tissue for Research is available through a link in the DCP website.

Prior to study initiation, the informed consent document must be reviewed and approved by NCI, DCP, the Consortium Lead Organization, and the IRB at each Organization at which the protocol will be implemented. Any subsequent changes to the informed consent must be approved by NCI, DCP, the Consortium Lead Organization's IRB, and then submitted to each organization's IRB for approval prior to initiation.

#### **14.6 Other**

This trial will be conducted in compliance with the protocol, Good Clinical Practice (GCP), and the applicable regulatory requirements.

### **15. FINANCING, EXPENSES, AND/OR INSURANCE**

The costs of all procedures for this protocol are paid for by the study contract with the exception of a pre-randomization standard of care staging PET/CT, a standard of care diagnostic biopsy, clinical

histopathology and the costs associated with surgical treatment of the oral/oropharyngeal for those study participants undergoing surgical treatment of their cancer at their end of study visit. If, at the time of surgery, there are added costs for the collection of the 4 mm tumor and visually appearing normal adjacent tissue during surgery, those added costs will be paid for by the study contract. In the event that a participant is physically injured as a result of participating in this research, there is no provision for compensation for medical care for the injury.

**APPENDIX A: PERFORMANCE STATUS CRITERIA**

**ECOG Performance Status Scale**

Grade	Descriptions
0	Normal activity. Fully active, able to carry on all pre-disease performance without restriction.
1	Symptoms, but ambulatory. Restricted in physically strenuous activity, but ambulatory and able to carry out work of a light or sedentary nature ( e.g. , light housework, office work).
2	In bed <50% of the time. Ambulatory and capable of all self-care, but unable to carry out any work activities. Up and about more than 50% of waking hours.
3	In bed >50% of the time. Capable of only limited self-care, confined to bed or chair more than 50% of waking hours.
4	100% bedridden. Completely disabled. Cannot carry on any self-care. Totally confined to bed or chair.
5	Dead.

**APPENDIX B: PILL DIARY**

UWI2016-07-01: Phase IIB Randomized, Placebo-Controlled Trial of ACTOplus met® XR in Subjects with Stage I-IV Squamous Cell Carcinoma of the Oral Cavity or Oropharynx Prior to Definitive Treatment	PID#: _____ Date: ___/___/_____
--	------------------------------------

PILL DIARY PAGE 1 of 3			
Dosing Instructions:	
Take one (1) tablet by mouth daily with a meal at approximately the same time each day.
 
Do not chew, cut or crush the tablets.
 
Do not take on an empty stomach.
 
Tablets are moisture and light sensitive. Keep the tablets tightly closed in their original container. Do not transfer to a pill organizer.
 
If you miss a dose, take it with your next meal on the same day. Do not make up a dose by taking two doses in one day.
		
Important Reminders:	Contact study staff immediately if you experience any of the following:		
	Nausea or Vomiting	Loss of appetite	Stomach pain
	Slow or irregular heartbeat	Unusual weakness or tiredness	Unusual muscle pain
	Trouble breathing (especially while lying down)	Swelling in the ankles or feet	Rapid weight gain
	Minimize use of alcohol:		
	Women:	No more than 3 drinks/day or more than 7 in a week.	
	Men:	No more than 4 drinks/day or more than 14 in a week.	
	One drink is:		
	Beer (12 oz.) 1 standard can or bottle	Wine (5 oz.) 1 standard glass	Spirits (6 oz.) 1 mixed drink or one 1.5 fluid oz. shot
	Check with study staff before taking any new medications to be sure the medication is not excluded for use while on this study.		
Notify study staff before having any scans (e.g. CT scan). The study medication should not be taken with the iodine containing dye used for some types of scans.			
Instructions for Completing the Pill Diary:	
Record the date and time you take your dose each day and initial each entry. In the Comments column:
 
 
• List any side effects or symptoms noticed.
 
• List any new medications taken and reason for taking
 
• If you missed a dose indicate why.
 
• Make a note if you've lost any pills
 
• Include any additional information you would like to note.
 
		

UWI2016-07-01: Phase IIB Randomized, Placebo-Controlled Trial of ACTOplus met® XR in Subjects with Stage I-IV Squamous Cell Carcinoma of the Oral Cavity or Oropharynx Prior to Definitive Treatment	PID#: _____ Date: ___/___/____
--	-----------------------------------

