2	
 
No modification unless the A.E. is unacceptable to the participant or the physician feels it is in the participant's best interest medically.
 
If the A.E. may be related to dose timing, asses how the participant is dosing their study agent and if taking it at a different time of day or with a more substantial meal might help.
 
If dose modification is necessary because taking the agent with a more substantial meal did not improved the event and the participant finds it unacceptable or the physician feels it is in the participant's best interest medically, the participant may be instructed to take the study agent every other day.
 
If none of these measures is successful and the A.E. is unacceptable to the participant or the physician feels it is in the participant's best interest medically, study agent should be discontinued. However, the participant, if willing, should still be followed per the protocol schedule of events and have all study procedures conducted
 
	
 
If the A.E. may be related to dose timing, asses how the participant is dosing their study agent and if taking it at a different time of day or with a more substantial meal might help.
 
If the AE is unlikely to be related to dose timing or did not respond to taking the study agent at a different time of day or with a more substantial meal, instruct the participant to hold study agent until the AE resolves to <math>\leq</math> Grade 1 then re-start on an every-other-day dosing regimen.
 
If the AE recurs, discontinue study agent and do not re-start. However, the participant, if willing, should still be followed per the protocol schedule of events and have all study procedures conducted.
 

3	Hold study agent until consulting with the protocol's medical monitor and study chair. The medical monitor and study chair will advise whether study agent may or may not be restarted and whether a dose modification is indicated.	Discontinue study agent. Do not re-start. However, the participant, if willing, should still be followed per the protocol schedule of events and have all study procedures conducted.
4		

Hypoglycemia (The symptoms include):		
Sweating, chills and clamminess	Nervousness/shakiness/anxiety	Hunger and nausea
Irritability/impatience/confusion	Weakness/fatigue	Rapid/fast heartbeat

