Numbness/tingling in the lips or tongue	Blurred/impaired vision	Sleepiness
Anger/stubbornness/sadness	Lightheaded/dizziness	Headaches
Nightmares/crying out during sleep	Lack of coordination	Seizures/ Unconsciousness

If a participant reports symptoms of hypoglycemia, instruct them to have their blood glucose level checked if possible:
 
 
• If the blood glucose level is less than the lower limit of normal but <math>\geq 55</math>mg/dL (grade 1 hypoglycemia), instruct the participant to switch to every other day dosing of the study agent. If this does not alleviate the participant's symptoms, instruct the participant to stop taking the study agent.
 
• If the blood glucose level is <math><55</math>-40 mg/dL (grade 2 hypoglycemia), instruct the participant to stop taking the study agent.
 
• If the participant is unable to have their blood glucose checked, base the dose modification on the severity of their symptoms. 
 
○ If the participant is experiencing grade 1 symptoms, and taking the study agent with a more substantial meal has not improved the symptom(s), instruct the participant to switch to every other day dosing. If this does not alleviate the symptom(s), instruct the participant to stop taking the study agent.
 
○ If the participant is experiencing grade 2 symptoms, instruct the participant to stop taking the study agent.
 
 
 
		

*For immediate, short term management of hypoglycemic symptoms, instruct the participant to try one or more of the following:
 
 
• Eat a handful of raisins or candy
 
• Drink a glass of juice, milk, or a regular (non-diet) soda
 
• Eat a small snack
 
		

Jaundice: Discontinue study agent. Do not re-start. Perform liver function tests ASAP.
		

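### The pill diary's immediate-contact list omits most of the hypoglycemia symptoms, and jaundice, for which Section 5.6 sets dedicated rules, and no adverse-event check is scheduled between the Day 5-7 call and end of study

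*Combined protocol and SAP*

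**What the plan says.** **Section 5.6 (Dose Modification).** Below the general grade table there is a hypoglycemia block with a symptom list. Its trigger is participant report: "If a participant reports symptoms of hypoglycemia, instruct them to have their blood glucose level checked if possible". If no reading can be obtained, symptoms decide: "If the participant is unable to have their blood glucose checked, base the dose modification on the severity of their symptoms". Jaundice has a separate line: "Discontinue study agent. Do not re-start. Perform liver function tests ASAP". That line does not say who detects the jaundice.

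**Appendix B (Pill Diary), page 1.** Under its reminders the diary says "Contact study staff immediately if you experience any of the following" and gives nine items. Other side effects and symptoms are to be written in the comments column, with no instruction there to call. Section 7.2.12 gives the same direction at dispensing.

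**Section 6.2.** Immediate reporting is asked for signs and symptoms of congestive heart failure and lactic acidosis, the two boxed-warning risks. No equivalent instruction is given for hypoglycemia or jaundice.

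**Contacts during dosing.** The Section 7.1 schedule places adverse-event assessment at the Day 5-7 call and at end of study or early termination. The later reminder call (Section 7.3.2 and the Section 7.1 footnotes) concerns the timing of the final dose. Section 4.4 states that the interim phone contact replaces a visit. The metabolic panel is drawn at baseline and at end of study only. The diary is returned at the end-of-study visit (Section 5.7.2.1), and the final dose is taken the day before the end-of-study surgery or biopsy (Section 5.2.5).

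**The concern.** A rule that starts with a participant's report works only if the participant knows what to report and when. In the reviewed text, the diary is the document that tells participants which symptoms call for immediate contact, and its list differs greatly from the one on which the hypoglycemia rule acts. On the written instructions, a participant who becomes shaky and dizzy on Day 12 is told to write it down. Staff would see the entry once dosing had finished, when a dose-modification rule can no longer do anything.

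What is at stake is participant safety and consistency between the protocol and a participant-facing form. The sample size, the significance level and the Ki-67 comparison are not affected.

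**Working it through.** The plan gives no figure of its own on this point. The check is a comparison of two lists and a count of days.

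**1. List comparison.** Inputs: the hypoglycemia symptom entries in Section 5.6 and the immediate-contact items in Appendix B.

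| Section 5.6 entry (paraphrased unless quoted) | Covered by a diary item? |
|---|---|
| "Sweating, chills and clamminess" | No |
| Nervousness or shakiness | No |
| Hunger and nausea | Yes, the nausea part: "Nausea or Vomiting" |
| Irritability or confusion | No |
| Weakness or fatigue | Yes: "Unusual weakness or tiredness" |
| Fast heartbeat | No; the diary has "Slow or irregular heartbeat" |
| Tingling of lips or tongue | No |
| Blurred vision | No |
| Sleepiness | Only if tiredness is read as sleepiness |
| Anger or sadness | No |
| Dizziness | No |
| Headache | No |
| Nightmares | No |
| Poor coordination | No |
| Seizure or unconsciousness | No |

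- Strict reading: 2 of 15 covered, so 15 − 2 = 13 omitted (13/15 = 87%).
- Generous reading: 3 of 15 covered, so 15 − 3 = 12 omitted (12/15 = 80%).
- Jaundice: not mentioned in the diary list.

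**2. Where the diary list comes from.** Most of its nine items (breathing trouble, swelling, weight gain, muscle pain, stomach pain, weakness or tiredness) correspond to the heart failure and lactic acidosis symptoms in Section 6.2. The list follows Section 6.2, not the dedicated blocks of Section 5.6.

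**3. Dosing days without a scheduled adverse-event check.** Inputs: the call window of Days 5-7 (Section 7.3.1), and 10 to 21 planned doses with a maximum of 25 if the biopsy or surgery is delayed (Section 5.1). Taking the call at its latest, Day 7, unchecked days = last dosing day − 7.

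| Doses | Days after the call | Count | Share of dosing days |
|---|---|---|---|
| 10 | 8-10 | 10 − 7 = 3 | 3/10 = 30% |
| 21 | 8-21 | 21 − 7 = 14 | 14/21 = 67% |
| 25 (delayed procedure) | 8-25 | 25 − 7 = 18 | 18/25 = 72% |

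A call on Day 5 would add two days to each count.

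**4. Jaundice.** The rule names no reporter. No visit or laboratory test is scheduled between baseline and the end-of-study procedures, so detection during dosing would rest on the participant or an outside clinician. That is an inference from the schedule, not a statement in the protocol.

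**The case against.** The strongest reply is that the two lists do different jobs. Section 5.6 tells staff what to do once a symptom is reported. The diary list carries the boxed-warning risks for which Section 6.2 asks immediate reporting. Nothing in the protocol says the diary must reproduce Section 5.6, so a reader who infers a contradiction goes too far. This stands: it is a gap between a rule and the form that feeds it, and the diary's origin in Section 6.2 explains the gap without closing it.

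Other safeguards exist. The Day 5-7 call asks about adverse events and may prompt later reporting. A participant could raise a symptom on the reminder call, although no adverse-event item is assigned to it. Eligibility excludes a history of hypoglycemia, diabetes treated with insulin or an antidiabetic agent, and a history of liver disease, and it limits bilirubin, AST and ALT. The consent form may warn about both conditions; its absence from the reviewed text is not a defect of the plan. These points lower the likely consequence but do not change what the diary says.

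A reader might also multiply the pooled hypoglycemia frequency of 3.5% in Section 6.2 by the 26 participants planned on active agent. The documents do not support that. The figure comes from diabetes trials, whereas this population is screened and not on antidiabetic drugs. It is not confined to the days after the call, and Section 2.3.2 says metformin does not cause hypoglycemia when used as labeled. No expected number of cases is offered here.

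**Conclusion.** The point holds as a cheap improvement. The hypoglycemia rule depends expressly on participant report, while the immediate-contact list covers 2, at most 3, of its 15 symptom entries. Jaundice, which has its own rule, is absent from the list. The period without a scheduled adverse-event check is 3 to 14 dosing days on the planned schedule, counted from Day 7. The 18-day figure applies only at the 25-dose extension and should not be read as typical.

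Two stronger readings are not supported. One is that the rules would simply fail after Day 7: two of the listed symptoms would prompt a call, participants may report others unprompted, and the consent pages cannot be checked. The other is that the protocol makes the jaundice rule depend on participant report, which is only inferred from the lack of an interim visit or laboratory test.

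The conclusion assumes that participants receive no further written or spoken instruction on these symptoms. If the consent form already covers them, the remaining issue is alignment of the diary with it.

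**What to change.** Reconcile the Appendix B immediate-contact list with the two dedicated Section 5.6 rules (hypoglycemia and jaundice) and with Section 6.2. The sponsor should decide which symptoms to name and how to word them. The scope should stay with those two rules: Section 5.6 also sets actions for adverse events from grade 1 upward, so requiring every symptom on which any rule acts would have no natural limit and would dilute the boxed-warning items. No dose or stopping rule needs to change.

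The cost is one form revision with IRB approval and a somewhat longer contact list. The statistical sections need no amendment.
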